AE	Adverse Event/Adverse Experience
AEFI	Adverse Event Following Immunization
Anti-NP	Anti- nucleocapsid Protein
CC	Coordinating Centre
CIOMS	Council for international Organizations of Medical Sciences
CRF	Case Report Form
CTCAE	Common Terminology Criteria for Adverse Events
CTO	Clinical Trial Ontario
CCTS	Centre for Clinical Trial Support
CKD	Chronic Kidney Disease
COVID-19	Coronavirus 19
EC	Ethics Committee
ELISA	Enzyme Linked Immunosorbent Assay
HD	Hemodialysis
IB	Investigator's Brochure
ICH	International Council for Harmonisation of Technical Requirements for Pharmaceuticals for Human Use
IP	Investigational Product
DSMB	Data Safety Monitoring Committee
DSPC	1,2-distearoyl-sn-glycero-3-phosphocholine
eCRF	Electronic Case Report Form
pCRF	Paper Case Report Form
EDC	Electronic Data Capture

GCP	Good Clinical Practice
ICF	Informed Consent Form
MedDRA	Medical Dictionary for Regulatory Authorities
ORN	Ontario Renal Network
PD	Peritoneal Dialysis
PHI	Personal Health Information
PHIPA	Personal Health Information Protection Act
PI	Principal Investigator
PM	Product Monograph
QI	Qualified Investigator
RBD	Receptor-Binding Domain
REB	Research Ethics Board
RCT	Randomized Controlled Trial
SAE	Serious Adverse Event/Serious Adverse Experience
SC	Steering Committee
snELISA	Surrogate neutralization ELISA
SOP	Standard Operating Procedure
SRI	Sunnybrook Research Institute
SUADR	Serious and Unexpected Adverse Drug Reaction
TMF	Trial Master File
TDL	Task Delegation Log
USP	United States Pharmacopeia

Protocol Summary

Full Title	BOOST KIDNEY: A Multi-Centre 12 Month Parallel-Group Randomized Control Trial of BNT162b2 versus mRNA-1273 COVID-19 Vaccine Boosters in Chronic Kidney Disease and Dialysis Patients with Poor Humoral Response following COVID-19 Vaccination
Short Title	BOOST KIDNEY
Phase	II/III
Protocol Number	3750
Version Date	Version 5.0, Nov 5, 2021
Study Duration	1 year
Principal Investigator	[name]
Setting	Multicenter, 5 Dialysis Centres in Ontario and British Columbia, Canada
Number of Participants	300 participants
Study Design	Four arm parallel randomized controlled trial of BNT162b2 versus mRNA-1273, third dose of the COVID-19 vaccine stratified by initial two dose vaccine type
Main Inclusion Criteria	Dialysis and non-dialysis chronic kidney disease (Stage 3b-5)
Primary Outcome(s)	Evaluate effect of third dose COVID-19 vaccine booster (BNT162b2 versus mRNA-1273) on serologic SARS-CoV-2 response (Anti-RBD) at 1 month following booster dose.

Secondary Outcome(s)	
 1. Evaluate effect of third dose COVID-19 vaccine booster (BNT162b2 versus mRNA-1273) on Anti-Spike and SARS-CoV-2 viral neutralization at 1 month following booster dose. 2. Anti-Spike and Anti-RBD response at study enrolment, 3 months, 6 months and 12 months following booster dose. 3. Flow cytometry on PBMC, single-cell RNA sequencing and ELISPOT prior to, 1 month, and 6 months following booster dose to evaluate SARS-CoV-2 specific B and T-Cell response. 4. Evaluate adverse effects related to third dose of vaccine through a questionnaire 48 hours -14 days, and 30 days following third vaccine dose. 5. Differences in COVID-19 infections, symptomatic COVID-19 infections, hospitalization, and death between study groups.
Statistical Analysis	
Intention to treat analysis for the primary outcome with two Chi-Squared test or Fisher's exact test for the primary outcome. Non-parametric testing for differences in antibody level between study groups. Mixed effects models will be used for comparison of longitudinal antibody levels.

2 INTRODUCTION

This study document is the protocol for research involving human participants. This study is to be conducted according to Canadian and International standards, and in compliance with the protocol, the International Council for Harmonization of Technical Requirements for Pharmaceuticals for Human Use (ICH) Good Clinical Practice E6 (GCP), World Medical Association Declaration of Helsinki: Ethical Principles for Medical Research Involving Human Participants, as well as applicable regulatory and institutional requirements and research policies. This protocol was developed following the SPIRIT checklist for interventional trials.

As of July 1, 2021 there have been 1003 patients on chronic dialysis treatment who have been infected with COVID-19. Due to their comorbidities, patients on dialysis are at greater risk for severe COVID-19 disease. In Ontario, 63% of chronic dialysis patients with COVID-19 have required hospitalization, and the case fatality rate has been reported at 28.5%, which is almost 4 times higher than in the general population.⁴ This is consistent with a recent meta-analysis of 3261 hemodialysis patients who contracted COVID-19 and identified an overall mortality rate of 22.4%.⁵ Similarly, data from the European Renal Association–European Dialysis and Transplant Association Registry identified a COVID-19 attributable mortality of 20% in 3285 receiving dialysis.⁶

In general, dialysis patients are known to have decreased immune response to vaccination, including lower rates of seroconversion, lower antibody titers, and a less sustained humoral response after immunization compared with the general population. This is evident from routine Hepatitis B vaccination in dialysis patients wherein repeated series and booster doses are

required to maintain immunity.⁷ The rate of seroconversion following the hepatitis B vaccine is only 44% in dialysis patients.⁸ Furthermore, Hepatitis B antibody titers decline more rapidly in individuals who receive Hepatitis B immunization compared to individuals who acquire natural Hepatitis B infection.

Predictors of antibody levels against SARS-CoV-2 are under active investigation. A study in 98 dialysis patients infected with COVID-19 showed that COVID-19 specific antibody titers decreased significantly one month following seroconversion,¹⁰ which is remarkably shorter than the healthy general population wherein durable humoral immunity may last at least 4-8 months.¹¹

Both the *BNT162b2 mRNA Covid-19 Vaccine (COMIRNATY®/Pfizer-BioNTech)* and the *mRNA-1273 SARS-CoV-2 Vaccine (SPIKEVAX®/Moderna)* randomized placebo-controlled trials, included only limited patients with kidney disease and patients receiving immunosuppressive treatment were excluded.^{12,13}

2.2 Clinical Data to Date

Given this significant knowledge gap, we conducted the SMASH-COVID-19 Study (Serial Measurement of Quantitative COVID-19 Antibodies in Hemodialysis and Peritoneal Dialysis Patients following COVID-19 Vaccination) in hemodialysis patients at Sunnybrook Health Sciences Centre to determine their humoral response to vaccination. In this prospective observational study, humoral response was compared in 66 hemodialysis patients sampled 28 days after receipt of one dose of vaccine to 76 patients who received two doses of vaccine sampled 14 days after the second dose. Among those receiving one dose, 6% had anti-RBD response above the median level of convalescent serum versus 41% who received two doses after 28 days. Given this finding, it was concluded that hemodialysis patients exhibit a poor humoral response to a single dose of BNT162b2 vaccine and the second dose should not be

delayed.¹⁴ Furthermore, longitudinal follow-up at 13 weeks of our cohort of vaccinated hemodialysis patients has demonstrated that some individuals do not seroconvert and a significant proportion of individuals who attained convalescent serum levels of COVID-19 antibodies (anti-Spike and anti-RBD) exhibit declining antibody levels by 13 weeks as shown in Figure 1, which has not been observed in the general population. This single centre pilot study has led to a larger multi-centre study in Ontario and British Columbia entitled “Determining the Safety and Efficacy of COVID-19 Vaccination in the Chronic Kidney Disease Population” (CTO Protocol Number 3604) which is continuing to recruit patients with chronic kidney disease stage 3b-5. This study will follow serologic response to COVID-19 vaccination in patients with advanced chronic kidney disease including those on dialysis for a one year period to better understand the duration of humoral immunity in this patient population.

[figure not shown]

Figure 1: SARS-CoV-2 IgG Anti-RBD Response Following BNT162b2 Vaccine in Hemodialysis Patients up to 13 weeks following second dose of vaccine.

Patients have been divided into 5 clusters by k-clustering based on trajectory of anti-RBD response over time. Cluster 1 (orange) generally obtained robust response following vaccination

and maintains serologic response 13 weeks. Clusters 2 (yellow) had an Anti-RBD response but gradually exhibits declining titers, and 3 (green) was characterized by the presence of anti-RBD antibodies at the time of the second dose, either due to previous infection, response to the first dose, or both; in this group, most individuals retained antibodies at 13 weeks, similar to the Cluster 1 (orange), but some of the participants had more rapid decline in antibody levels. Cluster 4 (blue) generally did not achieve seroconversion following vaccination. Cluster 5 (purple) attained seroconversion but did not have an initial robust response defined as reaching convalescent serum levels and generally exhibits declining antibody levels over time. Antibody levels are reported as relative ratios to synthetic standards. Dots represent individual serum samples collected at the indicated times, and the samples from the same patients are connected by lines. Seroconversion threshold represents a positive test and is 0.186 and is indicated by the dashed line. The median level of antigen in convalescent serum taken 21-115 days post-symptom onset is considered a robust antibody response and is 1.25 for anti-RBD.

2.3 Rationale for Study

Given the concern that a proportion of dialysis patients do not reach convalescent serum antibody levels following two dose of COVID-19 vaccination, booster doses may represent a means of attaining improved humoral immunity analogous to what is currently practiced with Hepatitis B vaccines. At this time, there is limited data regarding humoral immunity in dialysis patients receiving booster doses and there are no studies examining cellular immunity after a booster dose. A study in France of 45 hemodialysis patients receiving a third dose of BNT162b2 COVID-19 vaccine one month following the second dose found that two out of five patients who did not respond to two doses of vaccine had a robust response following the third dose. It was also noted that the median increase in antibody titers was >580% following the third dose.¹⁵

Early studies of booster doses in other vulnerable patient populations including transplant patients on immunosuppression have also emerged. A case series in 30 solid organ transplant patients receiving a third dose of vaccine included 24 patients with negative antibody titers, and 6 with low-positive antibody titers. In this study, the third dose was provided a median of 67 days (IQR 59-81 days) following the second dose and different vaccine types were used for the third dose: Ad26.COV2.S vaccine (Johnson & Johnson/Janssen) in 15, mRNA-1273 vaccine (*SPIKEVAX®/Moderna*) in 9, and the *BNT162b2* (COMIRNATY®/*Pfizer-BioNTech*) in 6. Antibody testing against the spike or RBD protein at 14 days post third dose found that in those with low positive antibody levels, all had high positive antibody levels following the third dose. Among those with initial negative antibody levels, 6/24 (25%) were able to attain high-positive antibody levels. Adverse reactions recorded 7 days following third dose the incidence of severe symptoms was low, and the investigators concluded that their finding warranted clinical trials on booster doses in this patient population.¹⁶ Another recent study from France in solid organ transplant patients, including 78 kidney transplant candidates, also confirmed the utility of a third dose of the BNT162b2 vaccine in increasing the prevalence of patients with detectable SARS-CoV-2 antibody levels from 40% post second dose to 68% 4 weeks after the third dose. In this study, 44% of patients who were initially seronegative had seroconversion following the third dose. Notably those without antibody response were older and had lower GFR, which is typical of the hemodialysis population.¹⁷ Limited studies have examined cellular immunity, however a study which included 41 hemodialysis patients, 4 peritoneal dialysis patients and 35 healthy controls, and 40 kidney transplant patients found impaired memory B cell formation in dialysis patients including RBD-specific plasmablasts and post-switch memory B-cells when measured 3-4 weeks after second dose of vaccine.¹⁸

Therefore, we propose a multi-site randomized, participant and investigator blinded controlled trial with four parallel arms stratified by initial two dose vaccine received in chronic

kidney disease stage 3b-5, and patients with end stage kidney disease to determine whether vaccine boosters with a third dose of vaccine *mRNA-1273* vaccine (*SPIKEVAX®/Moderna*) or the *BNT162b2* (*Pfizer/BioNTech*) will enhance the humoral and cellular immunity in patients with kidney disease who have not-responded well to vaccination (defined as levels that are below the median convalescent level of anti-RBD). This may mean that a patient never attained convalescent serum level of anti-RBD or that they initially obtained convalescent serum levels but exhibit declining levels over time.

The four study arms in this study will be as follows (as shown in Figure 2):

1. Group 1: First two dose *BNT162b2*, Third dose *BNT162b2*
2. Group 2: First two dose *BNT162b2*, Third dose *mRNA-1273*
3. Group 3: First two dose *mRNA-1273*, Third dose *BNT162b2*
4. Group 4: First two dose *mRNA-1273*, Third dose *mRNA-1273*

This study will evaluate both the humoral and cellular immune response in these patients. Serologic will be collected prior to booster dose, 1 month, 3 months, 6 months and 12 months following booster dose. Based on experience and high patient engagement from our prior pilot study measuring humoral response to COVID-19 vaccination, we anticipate >70% of participants approached for this study will agree to participate.

Studies have suggested that heterologous priming COVID-19 vaccination may result in improved immunogenicity although reactogenicity may be increased as demonstrated by Com-COV study from the United Kingdom, which examined heterologous schedules incorporating an adenoviral-vectored vaccine (ChAd) and an mRNA vaccine (BNT162b2), randomizing to eight groups: ChAd/ChAd, ChAd/BNT, BNT/BNT or BNT/ChAd, administered at 28- or 84-day intervals. The trial failed to meet pre-specified non-inferiority for the BNT/ChAd regimen, but did demonstrate that the Geometric Mean Concentration was higher in heterologous combinations than the licensed ChAd/ChAd schedule.^{19,20} Another study from the United Kingdom in 88 health

care workers who received ChAd as their first dose and either a homologous boost with 9-12 weeks later with ChAd (n=37) or mRNA-1273 (n=51) found that 7-10 days following second dose Anti-RBD IgG levels were 5 times higher than pre-second dose with ChAd compared to 115 time higher with a mRNA-1273 boost. Similarly, this strong serologic response with heterologous vaccination was reflected in *in vitro* neutralizing antibody titers which were 20 times higher with heterologous vaccination with mRNA-1273 compared to approximately double following a second dose of ChAd compared to pre-second dose titers.²¹ Therefore in this study, heterologous vaccination for the third dose will be explored in comparison to receiving the same vaccine (homologous) for all three doses with the hypothesis that the heterologous vaccination will result in higher antibody levels.

3 STUDY OBJECTIVES

3.1 Primary Objectives/Outcomes

Determine the effect of a third dose of COVID-19 vaccine (*mRNA-1273* or *BNT162b2*) on humoral immune response in patients with chronic kidney disease stage 3b-5 including end stage kidney disease receiving dialysis who did not attain convalescent serum levels or exhibiting declining antibody levels below convalescent serum levels of Anti-RBD through measurement of Anti-RBD at 1 month (30 days) following third dose of vaccine.

3.2 Secondary Objectives/Outcomes

1. Measurement of Anti-Spike, Anti-NP antibodies, and SARS-CoV-2 specific neutralization at 1 month (30 days) following third dose of vaccine.
2. Determine the effect of a third dose of COVID-19 vaccine on humoral immune response in hemodialysis patients who did not attain convalescent serum levels or exhibiting declining antibody levels below convalescent serum levels of Anti-RBD through measurement of Anti-Spike, Anti-RBD, and Anti-NP antibodies at 3 months, 6 months and 12 months following booster dosage.
3. In a subset of participants, assess cellular immunity through flow cytometry on PBMC and single-cell RNA sequencing prior to, one month, and 6 months following vaccine booster.
4. Evaluate adverse events related to third dose of vaccine through a questionnaire within 48 hours to 14 days and 30 days following third vaccine dose.
5. Differences in COVID-19 infections, symptomatic COVID-19 infections, hospitalization, and death between study groups.

4 STUDY DESIGN

4.1 General Design

The BOOST-KIDNEY study is a prospective, investigator and participant blinded randomized four parallel arm controlled study for CKD stage 3b-5 patients to evaluate the effect of a booster dose of vaccine on immunogenicity among those who did not respond defined as not reaching convalescent serum levels of Anti-RBD, or who exhibit declining antibody titers below the convalescent serum level of Anti-RBD. Enrolment will prioritize patients on dialysis but inclusion criteria will also include non-dialysis CKD stage 3b-5. Patients who are already participating in the study “Determining the Safety and Efficacy of COVID-19 Vaccination in the Chronic Kidney Disease Population” (CTO Protocol Number 3604) and have been found to have poor humoral response to COVID-19 vaccination will prioritize for recruitment. However, if a booster dose of COVID-19 vaccine is approved for the study population during the study period, patients will be eligible without serologic evaluation.

Patients will be randomized to mRNA-1273 SARS-CoV-2 Vaccine (*SPIKEVAX®/Moderna*), or BNT162b2 mRNA Covid-19 Vaccine (*COMIRNATY®/Pfizer-BioNTech*) administered by a trained vaccine administrator. Information on prior vaccines received will be recorded, and patients may have received either mRNA-1273 SARS-CoV-2 Vaccine (*SPIKEVAX®/Moderna*), or BNT162b2 mRNA Covid-19 Vaccine (*COMIRNATY®/Pfizer-BioNTech*) for their initial two doses of vaccine. Patients will be stratified by their initial vaccine type (BNT162b2 or mRNA-1273) prior to randomization, which will result in four study groups as shown in Figure 2.

A placebo arm is not included in this study as it was not felt to be ethically justified, but comparison will be made to participants not receiving a booster vaccine enrolled in CTO Protocol Number 3604 who choose not to participate. Similarly a primary outcome of COVID-19 infection

or hospitalizations was not chosen given the low incidence of COVID-19 infections in Canada due to high vaccination rates in the country.

Prior to receiving a third vaccine dose, quantitative SARS-CoV-2 IgG antibody levels against the full-length spike protein S1 domain, and Receptor Binding Domain (RBD) to assess humoral response will be measured and Anti-SARS-CoV-2 nucleocapsid protein to measure evidence of prior COVID-19 infection. In addition, we will isolate peripheral blood mononuclear cells in a subset to evaluate cellular immune response, however this will only be performed at University Health Network and Sunnybrook Health Sciences Centre as only these centres have the capacity for processing these samples. A neutralization antibody assay developed by the [name] lab will also be used to assess for viral neutralization prior to booster dose at 1 month (30 days) post third dose of vaccine.

[figure not shown]

Figure 2: Four study groups in the BOOST KIDNEY study. Study participants will be randomized 1:1 after stratification by initial vaccine type.

Following the intervention, SARS-CoV-2 antibodies will be measured 1 month, 3 months, 6 months and 12 months post booster vaccination. Neutralizing antibodies will be measured at baseline and 1 month post third dose of booster vaccine. Cellular immunity in a subset will be evaluated at baseline, 1 month and 6 months post third dose of booster vaccine. Adverse events related to third dose of vaccination will be surveyed in the 14 day period following third dose of vaccine, and again 1 month following third dose. The study protocol may be altered if booster doses become available that are intended to target new SARS-CoV-2 variants. Furthermore, the study design will be adaptive, as if patients do not respond to a third dose of vaccine the study protocol may be amended to consider other vaccine booster interventions. All study practices will follow social distancing measures currently recommended by Public Health authorities.

5 PARTICIPANT SELECTION and WITHDRAWAL

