5.2 Inclusion Criteria

Each participant must meet all of the following inclusion criteria to participate in this study:

1. Patients with CKD stage 3b-5 defined as an eGFR of less than 45ml/min/1.73m² or less will be eligible. Stage 5 CKD will include patients receiving in-centre hemodialysis, home dialysis (home hemodialysis or peritoneal dialysis), at Sunnybrook Health Sciences Centre, Unity Health Toronto, University Health Network, Scarborough General Hospital, or the University of British Columbia vaccinated with two doses of the COVID-19 vaccine will be eligible for a third dose to be given 2-12 months following the second dose. Patients may have participated in another COVID-19 study (CTO Protocol Number 3604) to assess humoral response .Patient not currently in CTO Study Number 3604 who are interested in the study are also eligible for recruitment into that trial.
2. All participants will be age ≥ 18 at the time of study enrolment.
3. The participants informed consent is obtained.

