5.3 Exclusion Criteria

All participants meeting any of the following exclusion criteria at baseline will be excluded from participation in this study:

1. Patients not vaccinated against COVID-19 vaccination.
2. Patients who received heterologous first two doses of vaccine (expected to be a minimal number in this population as almost all patients received the same vaccine for both doses due to vaccination in dialysis units).
3. Patients with severe allergic reaction to prior COVID-19 vaccination or any of the ingredients.
4. New COVID-19 infection following study enrolment as determined by Anti-NP (drawn upon study enrolment) or new positive RT-PCR.

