5.4 Participant Selection

Approximately 300 patients on dialysis, CKD stage 3b-5, will be recruited for the study.

Serologic eligibility criteria for the study must be met following the screening period in the study.

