5.5 Participant Recruitment

Participants will be recruited from participating renal centers within Canada from patients who have received two doses of COVID-19 vaccine. Eligible patients already participating in “Determining the Safety and Efficacy of COVID-19 Vaccination in the Chronic Kidney Disease Population” (CTO Protocol No. 3604) will be approached, but patients not in CTO Protocol No. 3604 will also be screened for eligibility and participation. Patients with known poor humoral response based upon their serum Anti-RBD levels will be prioritized for recruitment into the trial,

but if a booster dose of COVID-19 vaccine is approved for the study population during the study period, all participants meeting the inclusion and exclusion criteria will be approached.

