7 STUDY SCHEDULE AND PROCEDURES

7.1 Study Procedure

Participants who meet study eligibility criteria and consent to participate will be enrolled in the study. At study enrolment baseline, serum will be collected for SARS-CoV-2 serology, neutralizing antibodies and in a subset determined by the Investigator, PBMC will be collected for assessment of cellular immunity at Sunnybrook Health Sciences Centre or University Health Network prior to receiving the booster dose. Patients who are already participating in the study “Determining the Safety and Efficacy of COVID-19 Vaccination in the Chronic Kidney Disease Population” (CTO Protocol Number 3604) and have been found to have poor humoral response to COVID-19 vaccination will be prioritized for recruitment. However, if a booster dose of COVID-19 vaccine is approved for subsets of the study population or the study population at large during the study period, patients remain eligible for randomization without serological confirmation of low antibody titres.

Vaccine will be administered by an individual trained in vaccine administration at the site.

Following vaccination, participants will be asked about adverse symptoms related to COVID-19 vaccination through a questionnaire at 48 hours -14 days either in person in the dialysis unit or by telephone and at 1 month post third dose.

Following the intervention with either third dose of booster vaccine, the participant will have blood collection for Anti-SARS-CoV-2 IgG antibodies targeting the full length spike protein, RBD, nucleocapsid protein at 1 month, 3 months, 6 months, and 12 months following receipt of the booster dose. For feasibility, neutralizing antibodies will only be performed at 1 month following third dose. Non-dialysis participants may have bloodwork testing as part of routine

clinical care at each time point to determine if the booster vaccine dose has impacted kidney function including a serum creatinine and a spot urine micro-albumin creatinine ratio.

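### If a booster is approved mid-study the low anti-RBD entry check is waived, yet the primary endpoint has no baseline condition, so participants already at 1.25 or above can count as responders in either arm

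*Combined protocol and SAP*

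**What the plan says.** **Target population.** Section 2.3 describes patients "who have not-responded well to vaccination (defined as levels that are below the median convalescent level of anti-RBD". The primary objective in section 3.1 concerns those "who did not attain convalescent serum levels or exhibiting declining antibody levels below convalescent serum levels of Anti-RBD". Section 6.1.3.1 puts that level at 1.25 for anti-RBD.

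**Waiver.** Section 4.1 states that "if a booster dose of COVID-19 vaccine is approved for the study population during the study period, patients will be eligible without serologic evaluation". Section 7.1 says that in this event "patients remain eligible for randomization without serological confirmation of low antibody titres", and section 5.5 says that "all participants meeting the inclusion and exclusion criteria will be approached". Those criteria set no anti-RBD limit: section 5.2 asks for kidney disease stage, age, consent and two prior doses, and the serologic item in section 5.3 concerns anti-NP.

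**Text without the exception.** Section 6.1.3.1 still uses the enrolment sample to confirm a low anti-RBD level. Section 5.4 says "Serologic eligibility criteria for the study must be met following the screening period in the study" but names no antibody, so it could refer to anti-NP alone. The closing sentence of section 6.1.3.1 reads mainly as making a low level sufficient for entry, and it accepts a value already held from study 3604.

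**Endpoint and analysis.** Section 10.5.1 takes the proportion at the convalescent anti-RBD level at 1 month, by intention to treat, with one chi-squared or Fisher test in each initial-vaccine stratum. New COVID-19 infection is the only exclusion. The footnote to Table 2 defines response in the same way. Neither place mentions the pre-booster level.

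**The concern.** Widening enrolment after an approval is a deliberate choice and is not the problem. The problem is that the objective and the endpoint were not adapted to it. Under the default rule everyone starts below 1.25, so being at 1.25 a month later is a response to the booster. Under the waiver some participants may start at or above 1.25. If they stay there they are counted as responders whichever vaccine they receive, and they carry no information about the difference between vaccines on this endpoint.

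Two things are at stake. The difference between arms shrinks, and power with it. The primary result would also describe a population that only partly matches the objective in section 3.1. The cited 25% response in section 10.2 comes from seronegative patients, so the base case of the sample size also presupposes a low starting level.

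**Working it through.** **Inputs from the plan (sections 10.2 and 10.5.1, Table 2).** Two-sided alpha 0.05 for each stratum test; 80% power; 25-point difference; base case 25% (BNT162b2) versus 50% (mRNA-1273); target 300; up to 10% loss; four groups.

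**Assumptions of this check.** Four equal groups. A share f of each group is at or above 1.25 before the booster and still there at 1 month. The remaining participants respond at the planned rates a and b.

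**Step 1: reproduce the plan's figure.** Pooled-variance formula without continuity correction, with p̄ = (a + b)/2:

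n = [1.96·√(2p̄(1 − p̄)) + 0.84·√(a(1 − a) + b(1 − b))]² / (b − a)²

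For 25% versus 50% this gives 57.7, so 58 per group and 4 × 58 = 232, as stated. It also returns Table 2's 58 for 50% versus 75% and 43 for 65% versus 90%.

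**Step 2: evaluable number.** 300 × 0.9 / 4 = 67.5 per group.

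**Step 3: dilution.** p1 = f + (1 − f)a and p2 = f + (1 − f)b, so p2 − p1 = (1 − f)(b − a). The 25-point difference becomes 22.5, 20 and 17.5 points at f = 10%, 20% and 30%.

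**Step 4: power.** Power = Φ{[(p2 − p1)√n − 1.96·√(2p̄(1 − p̄))] / √(p1(1 − p1) + p2(1 − p2))}, with p̄ now the mean of p1 and p2. Example, base case at f = 20%: p1 = 40%, p2 = 60%, (1.643 − 1.386)/0.693 = 0.371, power 64.5%.

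All randomised, n = 67.5 per group:

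| Planned rates | f = 0 | 10% | 20% | 30% | Power below 80% from |
|---|---|---|---|---|---|
| 25% vs 50% | 85.9% | 75.6% | 64.5% | 53.6% | f = 5.9% |
| 50% vs 75% | 85.9% | 79.6% | 72.2% | 64.0% | f = 9.4% |
| 65% vs 90% | 94.4% | 91.1% | 86.5% | 80.4% | f = 30.6% |

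Restricted to those below 1.25, n = 67.5 × (1 − f) per group at rates a and b:

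| Planned rates | f = 0 | 10% | 20% | 30% |
|---|---|---|---|---|
| 25% vs 50%, and 50% vs 75% | 85.9% | 82.0% | 77.3% | 71.5% |
| 65% vs 90% | 94.4% | 92.0% | 88.6% | 84.0% |

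The gain from restriction at f = 10% is 6.4, 2.4 and 0.9 points for the three pairs of rates; at f = 20% it is 12.8, 5.1 and 2.1 points.

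**What the documents say about f.** They give no value. The pilot's 41% (section 2.2) and 60% (section 10.2) above the convalescent level were measured early after the second dose. The booster follows 2 to 12 months after that dose, titres were falling by 13 weeks, and poor responders are recruited first. The pilot figures therefore do not estimate f.

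**The case against.** - **The harm depends on two unknowns.** It needs an approval during enrolment, and f is the share enrolled after approval times the share of those who are above 1.25 and stay there. If half enrol after approval and 20% of them are above, f = 10%. If 10% are above, f = 5%, and power is 80.9%, 82.9% and 92.9% for the three pairs of rates, all still over 80%. This stands: the size is illustrative.
- **Inference remains valid.** Randomisation protects the comparison, with no directional bias and no inflation of type I error. This stands.
- **The wording may imply a low start.** Attaining or reaching a level suggests beginning below it. No rule puts that reading into effect, and an intention-to-treat analysis with one named exclusion points the other way.
- **The entry texts may be a general rule with a stated exception.** That is a fair reading of sections 4.1 and 7.1 against 6.1.3.1. It makes the entry conflict mostly editorial but leaves the endpoint gap untouched.
- **Other parts of the plan help.** Section 10.5.1 allows logistic adjustment, but only if imbalance is found. The quantitative antibody comparisons in section 10.5.2 are secondary. The subgroups in section 10.5.3 are exploratory, and none isolates participants still at or above 1.25. Section 10.5 leaves a final analysis plan to be written. None of these defines the primary set.
- **Restriction gains little when response is high.** This is true, and higher rates are plausible: section 10.2 cites 100% response in low-positive transplant patients.

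**Conclusion.** The concern holds and should be fixed, with medium confidence about its practical size. As written, once a booster is approved, participants at or above 1.25 can enter and count as responders in both arms, while the objective remains limited to those below. The question is diluted rather than replaced.

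In the plan's base case an f of about 6% is enough to bring power below 80%. At 50% versus 75% the figure is about 9%, and at 65% versus 90% about 31%. These results rest on equal strata, 10% loss, an assumed f, and all above-threshold participants staying above. If no approval occurs during enrolment and low anti-RBD is confirmed before the booster, the problem does not arise.

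**What to change.** 1. In section 10.5.1, before any unblinded analysis, define the primary population as randomised participants whose pre-booster enrolment anti-RBD is below 1.25. State that this sample governs over earlier study 3604 values, and give a rule for a missing enrolment value.
2. Report all randomised participants as a secondary analysis adjusted for baseline log anti-RBD. Wider enrolment can continue.
3. Alternatively, if everyone is to be in the primary test, widen the objective in section 3.1 and restate the sample size for the diluted difference.
4. Reconcile sections 4.1, 5.2, 5.4, 5.5, 6.1.3.1 and 7.1 so that they state one entry rule.

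**Cost.** Wording only. Table 1 already schedules anti-RBD at enrolment, and assigned vaccine cannot affect a pre-booster value, so the randomised comparison is preserved. The downside is that above-threshold participants leave the primary test. Restricted power stays at 80% only up to about f = 14% in the first two rows (1 − 58/67.5) and about 37% in the third; beyond that the stated power needs revising.

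Enrolment for 80% power with 10% loss is 4 × 58 / 0.9 / (1 − f) under restriction (43 in place of 58 for the third row), and 4 × n(p1, p2) / 0.9 for all randomised:

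| Planned rates | Restricted, f = 10/20/30% | All randomised, f = 10/20/30% |
|---|---|---|
| 25% vs 50% | 287 / 323 / 369 | 338 / 432 / 556 |
| 50% vs 75% | 287 / 323 / 369 | 307 / 365 / 440 |
| 65% vs 90% | 213 / 239 / 274 | 218 / 254 / 298 |
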